7.2 Follow-up

- See COG Late Effects Guidelines for recommended post treatment follow-up:
<http://www.survivorshipguidelines.org/>

8.0 CRITERIA FOR REMOVAL FROM PROTOCOL THERAPY AND OFF STUDY CRITERIA

8.1 Criteria for Removal from Protocol Therapy

- Progressive disease (see definition in Section 10.4).
- Significant toxicity at least possibly attributed to Pegylated interferon despite two dose reductions (as stated in Section 5.0).
- Refusal of further protocol therapy by patient/parent/guardian.
- Completion of 26 cycles of protocol therapy.
- Physician determines it is in patient's best interest.
- Development of a second malignancy.
- Patient becomes pregnant while on study.

Patients who are off protocol therapy are to be followed until they meet the criteria for Off Study (see below). Follow-up data will be required unless consent was withdrawn.

8.2 Off Study Criteria

- Death.
- Lost to follow-up.
- Patient enrollment onto another treatment study with tumor therapeutic intent.
- Withdrawal of consent for any further data submission.
- The fifth anniversary of the date the patient was enrolled on this study.

9.0 STATISTICAL CONSIDERATIONS

9.1 Sample Size and Study Duration

This study will enroll patients without NF-1 and patients with NF-1. Based on the established accrual goals and incidence of pediatric low grade gliomas 17 patients can be accrued within 36 months of protocol activation, given an average of 1 patient per 2.1 months. Assuming 15% of patients are not evaluable or eligible, 20 patients total will be required to be enrolled on this study.

9.2 Study Design

The study is designed using Simon's two stage optimal design with a power of 80% and an alpha error of 5%. We assume an uninterested response rate of 5% and the promising response rate is 25%. In the first stage of the study, 9 eligible patients will be enrolled. If none responder among the 9 patients, the study terminates and treatment will be determined to have no improvement in the response rate. Otherwise, the study will continue with the second stage in which 8 additional eligible patients will be enrolled for a total of 17 eligible patients. At the end of total patient accrual, at least 3 of 17 eligible patients must

achieve response in order to consider the treatment interesting for further evaluation. Response is considered as either CR or PR or SD.

Optimal Two Stage Design	Optimum Design
First Stage Sample Size (n1)	9
Upper Limit For 1st Stage Rejection of Drug (r1)	0
Maximum Sample Size (n)	17
Upper Limit for 2nd Stage Rejection of Drug (r)	2
Expected Sample Size If Response Probability = P0	11.96
Probability of Early Termination at P0	0.63

9.3 Methods of Analysis:

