1.0 OBJECTIVES

1.1 PRIMARY STUDY OBJECTIVES

To determine the objective response of children with recurrent or Refractory and radiographically or clinically progressive Juvenile Pilocytic Astrocytomas and Optic Pathway Gliomas who are treated with pegylated interferon alpha-2b Response will be determined as complete response or partial response.

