9.4 Analysis of Efficacy

Each patient will be classified according to their 'best response' for the purposes of analysis of treatment effect. A responder is defined as a patient who achieves a best overall response of CR or PR at any time on the study. If a patient achieves a PR or CR and later has progressive disease or relapse, then the patient will be counted as a responder. The response rate will be calculated as the ratio of the number of patients who demonstrate response (CR or PR) divided by the number of patients evaluable for response. All patients eligible for study who receive any study drug will be considered evaluable for response. Any patient who goes off protocol therapy for any reason (patient/parent/physician choice, adverse event profile, etc.) prior to the first response evaluation will be considered a non-responder. Disease progression will be based on the results of institutional review. Standard survival methods will be used for analysis of EFS and OS. Analyses include log rank tests and the product-limit (Kaplan-Meier) estimate for estimation of EFS and OS probability.

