9.5 Monitoring for Efficacy

Patients will be treated with Pegylated interferon on a single arm. We will closely monitor the first 9 patients enrolled. The early stopping criterion and the decision regarding ultimate further interest in this

agent will be based on the number of objective responses and disease progressions. If the early stopping rule is met for no responses in the first 9 patients, the trial will be closed.

A true response rate of 5% is considered inadequate, whereas a true response rate of 25% would be sufficient for further interest in this agent.

The study will be a 2-stage design, with 9 evaluable patients in the first stage and 8 additional evaluable patients in the second stage (17 patients total) with decisions made as follows:

Number of Evaluable Patients	Results	Decision
Stage One: 9 evaluable patients	zero responders	Terminate enrollment with the conclusion the regimen does not demonstrate sufficient disease control
Stage Two 8 evaluable patients	3 responders	Complete the trial with the conclusion the regimen does demonstrate sufficient disease control to proceed with further development.

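### Section 9.2 counts stable disease as response in the stop/go rule, while 1.1 and 9.4 count only CR or PR, so the stated 5% error rate does not hold for the objective-response endpoint

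*Combined protocol and SAP*

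**What the plan says.** Section 9.2 describes a Simon optimal two-stage design with 80% power and 5% alpha, an uninteresting response rate of 5% and a promising rate of 25%. Enrolment stops if none of the first 9 eligible patients responds. Otherwise 8 more are enrolled, and at least 3 responders among 17 make the treatment worth further study. The same paragraph ends with the definition to be used: "Response is considered as either CR or PR or SD".

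Other sections define response differently:

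- Section 1.1 (primary objective): "Response will be determined as complete response or partial response".
- Section 9.4: "A responder is defined as a patient who achieves a best overall response of CR or PR at any time on the study". The response-rate numerator in 9.4 is again CR or PR.
- Section 9.3.1.1 names the primary endpoint as objective response and refers to section 10 for the criteria. Sections 10.5 and 10.7 list SD as a category separate from PR.

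Section 9.5 repeats the 5% and 25% rates and the same cut-offs. Its text says the decision on the "agent will be based on the number of objective responses and disease progressions". Its table counts responders, but both rows state the conclusion in terms of disease control. The favourable row reads: "Complete the trial with the conclusion the regimen does demonstrate sufficient disease control to proceed with further development".

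**The concern.** The rates of 5% and 25% and the boundaries 0/9 and 2/17 carry their error rates only for the endpoint those rates describe. Adding SD to the count raises the observed rate by the SD rate, whatever the drug does.

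SD is a low bar in this protocol. Under 10.7 a target lesion whose three-diameter product has grown by just under 40% from its smallest value can still be SD. No minimum duration is given, and the first on-treatment scan is at the end of cycle 3 (7.1). Patients with NF-1 are eligible (3.2.2), and 2.1 says some lesions in NF-1 run an indolent course. The criteria listed in 3.2 require measurable residual disease but do not list documented progression at entry. SD without any drug effect is therefore plausible.

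A reader applying 9.2 would continue after one SD and no CR or PR among nine patients; a reader applying 9.4 would stop. Both would be following the protocol. If the conflict is settled after results are known, the choice of definition can follow the data and the 5% alpha cannot be defended. Under the SD reading, an inactive drug would also rarely be stopped at stage one.

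**Working it through.** **Inputs from 9.2.** n1 = 9, r1 = 0, n = 17 (so 8 in stage two), r = 2, p0 = 0.05, p1 = 0.25.

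**Assumed input.** The SD rate when the CR/PR rate is 5%. The documents give none, so 10%, 20%, 30% and 50% are shown. SD excludes CR and PR, so the rate counted under 9.2 is p = 0.05 + SD rate.

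**Formulas.**

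- Stage-one stop: PET(p) = (1 − p)^9
- Expected sample size: EN(p) = 9 + 8 × (1 − PET)
- Chance of a promising result: Go(p) = P(Bin(17, p) ≥ 3) − PET(p) × P(Bin(8, p) ≥ 3)

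The subtracted term removes the cases in which 3 or more of 17 would have responded but the trial had already stopped at 0 of 9.

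**Step 1: reproduce the plan's figures (CR/PR only).**

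- PET(0.05) = 0.95^9 = 0.630 (stated 0.63)
- EN(0.05) = 9 + 8 × 0.370 = 11.96 (stated 11.96)
- Go(0.05) = 0.0503 − 0.6302 × 0.0058 = 0.0466, within the 5% limit
- Go(0.25) = 0.8363 − 0.0751 × 0.3215 = 0.812, meeting 80% power

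A search over all designs with n from 5 to 30, alpha at most 5% and power at least 80% returns 0/9, 2/17 as the one with the smallest expected size at p0. The design is right for a 5% versus 25% endpoint.

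**Step 2: true CR/PR rate 5%, SD also counted.**

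| Assumed SD rate | Counted rate p | P(Bin(17, p) ≥ 3) | PET | P(Bin(8, p) ≥ 3) | Go(p) | EN |
|---|---|---|---|---|---|---|
| 0 (CR/PR only) | 0.05 | 0.0503 | 0.6302 | 0.0058 | 0.0466 | 11.96 |
| 10% | 0.15 | 0.4802 | 0.2316 | 0.1052 | 0.456 | 15.1 |
| 20% | 0.25 | 0.8363 | 0.0751 | 0.3215 | 0.812 | 16.4 |
| 30% | 0.35 | 0.9673 | 0.0207 | 0.5722 | 0.955 | 16.8 |
| 50% | 0.55 | 0.9997 | 0.0008 | 0.9115 | 0.999 | 17.0 |

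Unrounded, the 30% row is 95.54%, hence 96%. Go(p) reaches 0.95 at p = 0.343, an SD rate of 0.343 − 0.05 = 0.293. With an SD rate of 20%, a drug at the null CR/PR rate passes as often as the design intends for a drug at the target rate.

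**Step 3: how often the two definitions disagree.** A result that is promising on CR/PR is also promising once SD is added. The chance that 9.2 says promising and 9.4 does not is therefore Go(0.05 + SD) − Go(0.05):

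- SD 10%: 0.456 − 0.047 = 0.41
- SD 20%: 0.812 − 0.047 = 0.77
- SD 30%: 0.955 − 0.047 = 0.91
- SD 50%: 0.999 − 0.047 = 0.95

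**Sensitivity.** Ignoring the stage-one stop (3 of 17 in one stage) gives 5.0% for CR/PR only, 48.0% with 10% SD and 96.7% with 30% SD. The conclusion does not depend on how stage one is handled.

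**The case against.** The strongest reply is that the documents lean to CR/PR and that one sentence in 9.2 is an outlier. The primary endpoint is named objective response, 9.4 defines a responder as CR or PR and repeats it in the rate formula, and the 9.5 table counts responders. The disease-control wording there describes the conclusion about the regimen, not what is counted. This is a fair account of which definition was probably intended, and it is the reason to keep CR/PR. It does not remove the conflict: the outlying sentence sits in the paragraph that sets the boundaries, and no precedence rule exists.

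A second reply is that, read literally, 9.2 applies 5% and 25% to CR, PR and SD together. Alpha at that null is still 4.7%, so nothing is miscalculated. That is correct. On that reading the defect is different: nothing in the documents supports a 5% null or a 25% target for disease control. The inflated figures apply to a drug with a 5% CR/PR rate and should be read that way.

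Third, the SD rates are assumptions, and the results run from 46% to 99.9%. This stands as a limit on the size. Even the lowest rate shown raises the chance of a favourable result almost tenfold.

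Fourth, the disagreement probabilities partly compare hypothetical paths, because under CR/PR a trial with 0 of 9 would never enrol patients 10 to 17. That also stands; they are chances over two ways of running the trial.

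**Conclusion.** The concern holds. The plan gives two incompatible definitions of response for its only efficacy decision rule, and nothing in it says which one applies. With CR/PR the stated operating characteristics are correct. With SD counted they do not apply to a drug with a 5% CR/PR rate: the chance of a favourable conclusion is 46% to 99.9%, and the stage-one stopping chance 23% to 0.1%, over assumed SD rates of 10% to 50%. These figures rest on the assumed SD rates, on SD being exclusive of CR and PR, and on independent patients with a common rate. The contradiction itself needs no assumption. It must be corrected before the stage-one look.

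**What to change.** If CR/PR is the intended endpoint, as 1.1 and 9.4 indicate:

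- In 9.2, replace the sentence defining response with one stating that response is CR or PR as defined in 9.4.
- In both rows of the 9.5 table, replace the disease-control wording with sufficient objective response (CR or PR).
- In the 9.5 text, delete the reference to disease progressions or state how progressions enter the rule. This is a smaller, related point.
- Report CR, PR and SD combined as a descriptive result only.

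The cost is one sentence, two table cells and one phrase in a single amendment. Sample size, boundaries and procedures do not change.

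If the sponsor means SD to count, 1.1 and 9.4 must be aligned with 9.2. The null and target rates need justification for a disease-control endpoint that includes a minimum SD duration, and sample size and boundaries must be derived again from those rates.

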9.3.1 End Points

9.3.1.1 Primary End points:

- Objective response: best response determined from the sequence of objective status described in the section 10 as response criteria.

9.3.1.2 Secondary End Points

- Time to treatment failure (Event free Survival EFS) the time from study enrollment to tumor progression, tumor recurrence, death from any cause or occurrence of a second malignant neoplasm.
- Time to death (Overall survival OS) the time from study enrollment to death from any cause.

9.4 Analysis of Efficacy

Each patient will be classified according to their 'best response' for the purposes of analysis of treatment effect. A responder is defined as a patient who achieves a best overall response of CR or PR at any time on the study. If a patient achieves a PR or CR and later has progressive disease or relapse, then the patient will be counted as a responder. The response rate will be calculated as the ratio of the number of patients who demonstrate response (CR or PR) divided by the number of patients evaluable for response. All patients eligible for study who receive any study drug will be considered evaluable for response. Any patient who goes off protocol therapy for any reason (patient/parent/physician choice, adverse event profile, etc.) prior to the first response evaluation will be considered a non-responder. Disease progression will be based on the results of institutional review. Standard survival methods will be used for analysis of EFS and OS. Analyses include log rank tests and the product-limit (Kaplan-Meier) estimate for estimation of EFS and OS probability.

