10.9 Retrospective Response Review

MRI imaging for all patients on study will undergo retrospective central review following the completion of treatment.

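### A CR or PR on any single MRI counts as a response without having to persist, and the plan does not say whether the institutional or the central read decides the 3-of-17 conclusion

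*Combined protocol and SAP*

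**What the plan says.** All references are to the combined protocol and SAP.

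- **Responder.** Section 9.4 accepts a best overall response of CR or PR reached at any time on study, and continues: "If a patient achieves a PR or CR and later has progressive disease or relapse, then the patient will be counted as a responder". Sections 9.3.1 and 10.4 to 10.8 set no confirmation scan and no minimum duration.
- **Number of looks.** The table in 7.1 schedules MRI before cycles 4, 7, 10, 13, 16, 19, 22 and 25, and again at removal from therapy. That is at most nine readings, and response is judged against one baseline.
- **Who reads.** Section 9.4 states: "Disease progression will be based on the results of institutional review". It names no reader for response. Section 7.1 says only that MRIs are interpreted with the neuroradiologist. Section 10.9 adds: "MRI imaging for all patients on study will undergo retrospective central review following the completion of treatment". No section gives the result of that review a use.
- **Decision rule.** Section 9.2 describes a "two stage optimal design with a power of 80% and an alpha error of 5" (per cent), with response rates of 5% and 25%. The trial stops at 0 responders among 9. At the end, "at least 3 of 17 eligible patients must" respond for the drug to be taken further.
- **Thresholds.** In 10.7, PR is a fall of at least 65% in the three-diameter product. Where length cannot be determined, it is a fall of at least 50% in the two-diameter product. PD is a rise of 40% or 25% over the smallest value on treatment.

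**The concern.** The best of several unconfirmed readings against one baseline can only move the response count upwards, and the conclusion turns on three patients. There is no control arm in which the same error would appear. A PR that is absent 12 weeks later counts the same as a lasting one.

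The silence about the reader needs no assumption about error rates. Two reads of every MRI are planned. If they differ in one patient and the count is 2 on one and 3 on the other, the plan does not say which conclusion is the trial's result, and the choice could be made after both are known.

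**Working it through.** **1. The plan's own design.** Inputs from 9.2: n1 = 9, r1 = 0, n = 17, r = 2, p0 = 0.05, p1 = 0.25.

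P(go | p) = Σ over x = 1 to 9 of Bin(x; 9, p) × P(at least 3 − x responders among 8).

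- Early termination at p0: 0.95^9 = 0.630. Expected size: 9 + 8 × (1 − 0.630) = 11.96. Both agree with the table in 9.2.
- False-go at p0: 0.0171 (x = 1) + 0.0212 (x = 2) + 0.0084 (x ≥ 3) = 0.0466, or 4.7%.
- Power at p1: 0.812.

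**2. Effect of a false PR.** If a fraction q of true non-responders is recorded as PR at least once, the recorded rate at p0 is p = 0.05 + 0.95q, and false-go is P(go | p). The documents give no q. For an assumed over-call in 5% of non-responders, p = 0.05 + 0.95 × 0.05 = 0.0975 and P(go) = 21%.

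**3. Measurement error as a source of q.** The coefficient of variation (CV) per diameter is assumed, because the documents give none. The model is a truly unchanged single lesion, with independent lognormal error at baseline and at each of nine scans. The SD of the log product is √d × √ln(1 + CV²) for d diameters. PR is a ratio to baseline of 0.35 or less (d = 3) or 0.50 or less (d = 2). A patient leaves at the first reading that is 40% (d = 3) or 25% (d = 2) above the smallest so far, as 10.7 with 4.3 and 8.1 provides. There were 400,000 simulated patients.

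| Rule | CV | q | False-go, single scan | False-go, PR also on next scan |
|---|---|---|---|---|
| 3-D | 10% | <0.1% | 4.7% | 4.7% |
| 3-D | 15% | 0.8% | 6.7% | 4.8% |
| 3-D | 20% | 4.9% | 21% | 6.0% |
| 2-D | 10% | 0.1% | 4.9% | 4.7% |
| 2-D | 15% | 3.5% | 15% | 5.5% |
| 2-D | 20% | 10.8% | about 46% (47% in a repeat run) | 9.4% |

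Example, 3-D at 20%: p = 0.05 + 0.95 × 0.049 = 0.0966, giving P(go) = 21%.

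The same model calls 83%, 97% and 99% of stable patients progressive under the 3-D rule at the three CVs. At CV 20% the mean number of scans is 2.9, not nine.

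**4. Cost of confirmation.** If 5% of true responders cannot be confirmed, p = 0.25 × 0.95 = 0.2375 and power is 78.1%. If 10% cannot, p = 0.225 and power is 74.5%.

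**5. Different reads at the two stages.** The 0-of-9 look can only stop the trial. Whatever read it uses, false-go on the deciding read cannot exceed P(at least 3 of 17 at 5%) = 1 − (0.4181 + 0.3741 + 0.1575) = 0.0503, or 5.0%.

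**The case against.** The strongest reply is that the size rests on assumed error, and that the protocol limits it. The PR thresholds are wide. Section 10.4 requires the same plane and sequence at follow-up and does not let enhancement alone decide, and 9.10 asks for the same scanner where possible. Any CV large enough to matter under the 3-D rule would also label nearly every stable patient progressive, which makes such a CV doubtful. Success means only further evaluation, so confirmation is partly a matter of preference. Counting a responder who later progresses is ordinary best-response wording and could stay under a confirmed rule. All of this stands, and it keeps the point small.

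A reader might infer four stronger things that the documents do not support.

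- **That nine looks produce false responders in bulk.** Without removal at PD, the same model gives 4.7%, 8.5% and 38% (3-D) and 5.1%, 27% and 78% (2-D). Those figures ignore the protocol's removal rule. Section 4.4 would let some patients with PD continue, while 4.3, 8.1 and 10.4 take them off. Those passages must be reconciled, but they do not justify nine scans for everyone. The 2-D rule is also reserved for rare cases in 10.7, although 10.3 says length will not be used, a conflict that needs its own correction.
- **That targets go down to a fixed 8 mm.** Sections 10.3 and 10.6 give 8 mm only as an example for a 4 mm slice. The rule is twice the slice thickness.
- **That the 5% benchmark contains no unconfirmed responses.** Its source is not given. If it came from unconfirmed best responses, part of any inflation is already in it.
- **That the central review was meant to decide nothing.** The text is silent. It neither gives nor denies the review a role.

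What the reply leaves untouched is that no persistence is required and no deciding reader is named.

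**Conclusion.** The point holds as a cheap improvement. Two gaps are certain from the text: one reading of CR or PR on any MRI suffices, and the read that decides 3 of 17 is not named. Their effect on the false-positive rate is not known from the documents. With independent error in truly stable tumours and removal at PD, there is none at a CV of 10% or less. Under the 3-D rule it rises to about 6.7% at 15% and 21% at 20%; under the rarely used 2-D rule it rises to about 15% and 46%. An over-call in 5% of non-responders, also assumed, would give 21%.

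Confirmation removes most of the independent error. It does not remove all of a shared baseline misreading, nor a systematic over-read by one reader, which is why the deciding read also needs naming. These figures take response as CR or PR, as in 1.1 and 9.4; the sentence in 9.2 that adds SD is a separate inconsistency.

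**What to change.** **In 9.4:** for the primary analysis, count a CR or PR when it is still present on the next protocol MRI, whether scheduled or off-therapy. State that a response first seen on the last MRI is unconfirmed. Report the unconfirmed rate as a sensitivity analysis.

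**In 10.9:** name central review as the deciding read for 3 of 17, let the institutional read serve the 0-of-9 futility look, and report both response rates. Type I error on the deciding read then stays at about 5.0% or below (step 5).

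**Cost:** no new scan or read is needed, since the later MRIs and the central review are already planned. Power should be restated: about 78% or 75% instead of 81% if 5% or 10% of true responders cannot be confirmed (assumed shares). The final result also has to wait for the central read.

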9.5 Monitoring for Efficacy

Patients will be treated with Pegylated interferon on a single arm. We will closely monitor the first 9 patients enrolled. The early stopping criterion and the decision regarding ultimate further interest in this

agent will be based on the number of objective responses and disease progressions. If the early stopping rule is met for no responses in the first 9 patients, the trial will be closed.

A true response rate of 5% is considered inadequate, whereas a true response rate of 25% would be sufficient for further interest in this agent.

The study will be a 2-stage design, with 9 evaluable patients in the first stage and 8 additional evaluable patients in the second stage (17 patients total) with decisions made as follows:

Number of Evaluable Patients	Results	Decision
Stage One: 9 evaluable patients	zero responders	Terminate enrollment with the conclusion the regimen does not demonstrate sufficient disease control
Stage Two 8 evaluable patients	3 responders	Complete the trial with the conclusion the regimen does demonstrate sufficient disease control to proceed with further development.

